14.5.2. Reporting Serious Adverse Events

Any SAE, including death resulting from any cause, which occurs to any subject participating in this study must be reported via email or fax by the Investigator using the Endo Clinical Trial Report Form for SAEs within 24 hours of first becoming aware of the SAE. SAEs will be collected by the Investigator from the time of signing the informed consent through 30 days after the last dose of study medication. SAEs that occur within 30 days, following cessation of the study treatment, or within 30 days, following premature discontinuation from the study for any reason, must also be reported within the same timeframe. Any SAE that is considered by the Investigator to be related to the study medication must be reported regardless of the amount of time since the last dose received. Follow-up information collected for any initial report of an SAE must also be reported to the Sponsor within 24 hours of receipt by the Investigator.

All SAEs will be followed until resolution, stabilization of condition, or until follow-up is no longer possible.

In the event discussion is necessary regarding treatment of a subject, call the Medical Monitor (see contact information in section 3).

All SAEs should be sent via the email address, or faxed to the fax number, provided in section 3.

The Sponsor will determine whether the SAE must be reported within 7 or 15 days to regulatory authorities in compliance with local and regional law. If so, the Sponsor (or the Sponsor's representative) will report the event to the appropriate regulatory authorities. The Investigator will report SAEs to the institutional review board (IRB) per their IRB policy.

14.5.2.1. Follow-up Procedures for Serious Adverse Events

To fully understand the nature of any SAE, obtaining follow-up information is important. Whenever possible, relevant medical records such as discharge summaries, medical consultations, and the like should be obtained. In the event of death, regardless of cause, all attempts should be made to obtain the death certificate and any autopsy report. These records should be reviewed in detail, and the Investigator should comment on any event, lab abnormality, or any other finding, noting whether it should be considered a serious or non-serious AE, or whether it should be considered as part of the subject's history. In addition, all events or other findings determined to be SAEs should be identified on the follow-up SAE form and the Investigator should consider whether the event is related or not related to study drug. All events determined to be nonserious should be reported on the eCRF.

14.6. Special Reporting Situations

14.6.1. Adverse Events of Special Interest

[REDACTED]

14.6.2. Overdose/Misuse/Abuse

Study drug overdose is any accidental or intentional use of study drug in an amount higher than the dose indicated by the protocol for that subject. Study drug compliance (see section 12.3) should be reviewed to detect potential instances of overdose (intentional or accidental).

Any study drug overdose during the study should be noted on the study medication eCRF.

An overdose is not an AE per se, however all AEs associated with an overdose should both be entered on the Adverse Event eCRF and reported using the procedures detailed in section 14.5.2, Reporting of Serious Adverse Events, even if the events do not meet seriousness criteria. If the AE associated with an overdose does not meet seriousness criteria, it must still be reported using the Endo Clinical Trial Report Form for SAEs and in an expedited manner, but should be noted as non-serious on the form and the Adverse Event eCRF.

14.6.3. Pregnancy

Any uncomplicated pregnancy that occurs in a subject during this clinical study will **be reported for tracking purposes only**. All subject pregnancies that are identified during or after this study, where the estimated date of conception is determined to have occurred during study drug therapy or within 30 days of the last dose of study medication need to be reported, followed to conclusion, and the outcome reported, even if the subject is discontinued from the study. The investigator should report all pregnancies within 24 hours using the Initial Pregnancy Report Form, and any pregnancy-associated SAE using the SAE report form, according to the usual timelines and directions for SAE reporting provided in section [14.5.2](#). Monitoring of the pregnancy should continue until conclusion of the pregnancy; 1 or more Follow-up Pregnancy Report Form(s) detailing progress, and a Two Month Follow-up Pregnancy Report Form detailing the outcome, should be submitted.

Pregnancy itself is not regarded as an AE unless there is suspicion that the investigational product under study may have interfered with the effectiveness of a contraceptive medication. Likewise, elective abortions without complications are not considered AEs. Any SAEs associated with pregnancy (eg, congenital abnormalities/birth defects/spontaneous miscarriages or any other serious events) must additionally be reported as such using the SAE report form. Spontaneous miscarriages should also be reported and handled as SAEs.

Subjects should be instructed to immediately notify the investigator of any pregnancies.

Attempts to obtain the pregnancy follow-up and pregnancy outcome information detailed above are necessary even if a subject discontinues treatment because of pregnancy.

14.6.4. Adverse Events/Serious Adverse Events Experienced by Non-subjects Exposed to Study Medication

Non-subjects are persons who are not enrolled in the study but have been exposed to study medication, including instances of diversion of study medication. All such AEs/SAEs occurring in non-subjects from such exposure will be reported to the Endo Pharmacovigilance and Risk Management (PVRM) Department (when the non-subject agrees) on the departmental form for SAEs regardless of whether the event is serious or not. Instructions for completing the form for events experienced by non-subjects will be provided. SAEs occurring in non-subjects exposed to study medication will be processed within the same SAE reporting timelines as described in section [14.5.2](#), Serious Adverse Event Reporting. Additionally, the drug accountability source documentation at the site should reflect this occurrence.

14.7. Clinical Laboratory and Immunogenicity Determinations

Clinical laboratory tests will be conducted according to the Schedule of Events (section [5](#)). Clinical laboratory tests will be performed by a designated central laboratory. Each site will be provided with instructions on specimen collection, preparation, packaging and transport. Refer to the central laboratory manual for further information regarding sample collection, handling, and labeling. The results of the tests will be returned to the investigational sites.

Clinical laboratory test data will be reviewed by the investigator, or designee, and additional clinical laboratory tests may be ordered at his/her discretion (eg, if the results of any clinical laboratory test falls outside the reference range or clinical symptoms necessitate additional

testing to ensure safety). Any additional testing will be performed by the designated central laboratory.

The investigator will review all abnormal lab results for clinical significance. Any abnormal clinical laboratory test result meeting the investigator's or Sponsor's criteria for clinical significance (refer to central laboratory manual) will be recorded as an AE or SAE as appropriate (see section 14.1.1, Adverse Events or section 14.1.2, Serious Adverse Events).

Laboratory results will be sent electronically to Endo for data management.

Clinical laboratory parameters that will be measured in this study are listed in Table 11.

Table 11: Clinical Laboratory Parameters

Hematology	Clinical Chemistry	Urinalysis
Hematocrit	Blood urea nitrogen	Specific gravity
Hemoglobin	Creatinine	Ketones
Red blood cell count	Total bilirubin	pH
Red blood cell morphology	Alanine aminotransferase (ALT)	Protein
White blood cell count	Aspartate aminotransferase (AST)	Blood
Neutrophils	Alkaline phosphatase	Glucose
Lymphocytes	Sodium	
Monocytes	Potassium	
Basophils	Calcium	
Eosinophils	Chloride	
Platelets	Phosphate	
	Serum bicarbonate	
	Uric acid	
	Total cholesterol	
	Total protein	
	Glucose	
	Triglycerides	
	Albumin	

Female subjects of childbearing potential must have a negative urine pregnancy test at Screening B and at treatment visits 1, 2, and 3 (section 5) to receive treatment in the study. If necessary, additional urine pregnancy tests can be performed at any time during the study at the discretion of the Investigator.

14.7.1. Anti-AUX-I and Anti-AUX-II Antibodies

Serum samples will be collected and may be tested for binding and neutralizing anti-AUX-I and anti-AUX-II antibodies at Visit 4 of the observation assessments. Additionally, if a subject consents to treatment in the open-label study, serum samples for antibody testing will be collected before injection at treatment visit 1 and at end of treatment/early termination visit 4 of the open-label treatment period. A subset of subject samples may have neutralizing antibodies tested from Day 1 and Day 71 visits; additional samples may be analyzed if results or clinical signs warrant testing.

The serum samples obtained will be processed, stored and then shipped on dry ice to the designated central clinical laboratory before forwarding to Endo's appointed laboratory for the determination of anti-AUX-I and anti-AUX-II antibodies according to the Laboratory Manual.

14.8. Vital Signs

Vital sign measurements will be documented as described in the Schedule of Events. These parameters include pulse rate, respiratory rate, systolic and diastolic blood pressure, and body temperature. Pulse and blood pressure readings will be taken after the subject has been sitting for 5 minutes. Height should only be recorded at Screening B.

The investigator will review all vital sign values for clinical significance. Any vital sign value meeting the investigator's or Sponsor's criteria for clinical significance will be recorded as an AE or SAE as appropriate (see section 14.1.1, Adverse Events, and section 14.1.2, Serious Adverse Events).

For subjects receiving treatment, vital signs will be assessed at the time points shown in Table 12 after the subject has rested for at least 5 minutes.

The subject's vital signs should be stable, or repeated until stable before the subject can leave direct observation.

Table 12: Vital Signs Measurements on Injection Day

Time Point Relative to Last Injection	Blood Pressure, Respiratory Rate, and Pulse Rate	Body Temperature
Up to 4 hours (before treatment)	X	X
Approximately 15 minutes after	X	
Approximately 30 minutes after	X	X

14.9. Electrocardiogram

Performing a 12-lead electrocardiogram (ECG) is not necessary if Screening B visit date is within 12 months of obtaining an ECG during the double-blind study (EN3835-201).

If the date of Screening B visit is later than 12 months since obtaining the ECG in study EN3835-201, subjects will have a resting 12-lead ECG performed during the Screening B visit. A qualified physician will interpret, sign, and date the ECGs. Electrocardiogram assessments must be "within normal limits" or interpreted as "abnormal, not clinically significant" for the subject to be included in the study.

Any ECG result meeting the investigator's or Sponsor's criteria for clinical significance will be recorded as an AE or SAE as appropriate (see section 14.1.1, Adverse Events and section 14.1.2, Serious Adverse Events).

14.10. Physical Examination

Body weight will be collected as described in the Schedule of Events (section 5). If a subject desires treatment in the open-label study, a complete physical examination will be performed at Screening B. All examinations will be performed by a physician or health professional listed on the Form FDA 1572 and licensed to perform physical examinations.

The investigator will review all physical exam findings for clinical significance. Any physical exam finding meeting the investigator's or Sponsor's criteria for clinical significance will be recorded as an AE or SAE as appropriate (see section 14.1.1, Adverse Events and section 14.1.2, Serious Adverse Events).

14.11. Other Safety Assessments

Not applicable.

15. ASSESSMENT OF PHARMACOKINETICS

Not applicable.

16. ASSESSMENT OF PHARMACODYNAMICS

Not applicable.

17. STATISTICAL CONSIDERATIONS AND METHODS

17.1. Determination of Sample Size

Approximately 350 subjects that completed the EN3835-201 study will enroll in the current study. This sample size should be adequate to determine long term safety and cellulite assessments of EN3835.

17.2. Subject Cohorts and Subject Populations

Subjects will be classified into 1 of 4 different cohorts depending on where they receive the treatment of EN3835 in relation to where they received treatment in study EN3835-201. The 4 cohorts are:

1. Observational subjects only - subjects who received EN3835 in study EN3835-201 but do not receive any injections in the current study.
2. Re-treatment subjects - subjects who received EN3835 in study EN3835-201 and receive EN3835 in the current study in the same quadrant that was treated in the EN3835-201 study. This will only be allowed for subjects who have baseline severity ratings in the current study at or worse than the baseline seen in study EN3835-201 for both the CR-PCSS and PR-PCSS of the quadrant.
3. Re-dosing subjects - subjects who received EN3835 in study EN3835-201 and receive EN3835 in the current study in a quadrant different than the EN3835-treated quadrant in study EN3835-201.
4. Initial treatment subjects - subjects who received placebo in study EN3835-201 and receive EN3835 in the current study.

All efficacy and safety analyses will be done within the classified cohort. Durability of treatment effects is defined as the time from onset of change from baseline of PR-PCSS and CR-PCSS in the quadrant treated in study EN3835-201 [REDACTED], where possible, in which the treated quadrant returns to baseline cellulite severity ratings of PR-PCSS and CR-PCSS in an EN3835-treated quadrant. Durability will be determined for all subjects that were treated with EN3835 in either EN3835-202 or EN3835-201. If sequential visit [REDACTED] are not available for that quadrant due to retreatment or [REDACTED], then the singular time point at which ratings return to baseline will be the durability cessation date.

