9.2. Secondary Objectives

- To evaluate safety and immunogenicity of re-treating or re-dosing a subject that had previously received treatment with EN3835
- To evaluate the durability of response to EN3835 in EFP severity over the 12-month post initial dosing of EN3835 in subjects previously receiving active treatment in study EN3835-201 using the PR-PCSS and the CR-PCSS
- To evaluate the durability of response to EN3835 in EFP severity beyond 12 months post initial dosing of EN3835 in subjects previously receiving active treatment in study EN3835-201 using the PR-PCSS and the CR-PCSS
- To evaluate long-term response to EN3835 in assessments of EFP including subject satisfaction, I-GAIS, and S-GAIS
- To assess cellulite severity assessments in quadrants treated in this study with EN3835
- To evaluate immunogenicity after exposure to EN3835

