12.1.4. Treatment Assessments (Optional)

After unblinding of treatment assignment in the EN3835-201 study, subjects are eligible for optional treatment in the open-label study, provided they meet the inclusion and exclusion criteria detailed in section [11](#) and at least 1 quadrant meets the criteria for treatment. A subject may receive a maximum of 2 courses of treatment (6 treatment sessions) overall (total of treatments in double-blind and open-label study). If a subject received placebo in the double-blind study, she may be eligible for 2 treatment courses in the open-label study; if a subject received active drug in the double-blind study, she may be eligible for 1 additional treatment course (3 treatment sessions) in the open-label study.

Selection of Treatment Quadrant

During the Screening B visit, each subject will have photographs taken of the 4 targeted quadrants of the study (eg, their left and right buttocks and left and right posterolateral thighs). Subjects will receive instructions ([Appendix D](#)) for using the PR-PCSS and will use the scale to rate the severity of their cellulite in each of the 4 quadrants by comparing each of their digital image photographs with the PR-PCSS instrument. This self-assessment will take place in a private setting to minimize any potential bias from site personnel. The Investigator will then assess each of the subject's 4 quadrants live in real-time using the CR-PCSS. The Investigator will then examine each of the 4 quadrants live to assess the subject using the Hexsel CSS as described in section [13.1.1.6.\(12\)](#) Subjects must have at least 1 quadrant that meets the following criteria for treatment in the study:

1. PR-PCSS score of 3 or 4, and
2. CR-PCSS score of 3 or 4, and
3. Hexsel CSS score no greater than 13.

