After the independent assessments are completed separately by the subject and the Investigator, the Investigator will review his/her assessments and the subject's assessment to determine which quadrants, if any, are eligible. The eligible quadrants (must meet all 3 of the inclusion criteria (PR-PCSS, CR-PCSS, and Hexsel CSS scores), if any, for treatment will be determined by the Investigator after which the quadrant selected will be at the discretion of the subject. For subjects treated with EN3835 in the double-blind study, if the quadrant treated in the double-blind study (EN3835-201) has PR-PCSS and CR-PCSS ratings identical or more severe than the double-blind study (EN3835-201) PR-PCSS and CR-PCSS baseline ratings (Baseline is Day 1 of study EN3835-201), subjects can elect to have that same quadrant re-treated. Subjects who choose re-treatment of the previously treated quadrant will be classified in the re-treatment arm. If another quadrant besides the previously treated quadrant meets all 3 of the inclusion criteria, subjects can choose to be treated in the naive quadrant. Subjects who choose treatment into a naive quadrant will be classified in the re-dosing arm.

Assessments made with the PR-PCSS (from digital image), the CR-PCSS (live assessment), and the Hexsel CSS score during the open-label Screening B visit will be the baseline severity of EFP in the selected quadrant.

A subject who received placebo in the double-blind study may be treated in the same quadrant in the open-label study if the quadrant still meets all 3 criteria OR another qualifying quadrant may be selected for treatment by the subject. Following Day 71 of a treatment course (3 treatment sessions), subjects can choose to receive a second treatment session in either the same quadrant if it still meets qualification criteria or in a different quadrant that meets qualification criteria. For the first treatment course, these subjects will be considered in the treatment arm. For the second treatment course, if the same quadrant is treated, subjects will be in the re-treatment arm; if a different quadrant is treated, subjects will be considered in the re-dosing arm.

If no quadrant meets all 3 criteria, the subject may continue in the observation-only study with safety and cellulite severity evaluations performed at 3-month intervals but may not receive treatment in this study.

Selecting and Marking Dimples

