17.7. Immunogenicity Analyses

Immunogenicity variables include anti-AUX-I/anti-AUX-II binding antibody results. Binding antibody levels will be determined from samples collected on Days 1 and 71 during the treatment phase and Day 360 during the observational phase.

Descriptive statistics (percent of positive measurements and average antibody level) will be presented for anti-AUX-I and anti-AUX-II antibody levels at each time point by region treated and overall. Average antibody levels will be summarized on logarithmically transposed titer values.

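### Second EN3835 courses in former placebo subjects are classified one way in 12.1.4 and another in 17.2, and 17.7 sets no antibody summary by prior exposure, so the re-exposure objective is only partly answered

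*Combined protocol and SAP*

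**What the plan says.** The protocol (Amendment 4) has a secondary objective in 9.2: "To evaluate safety and immunogenicity of re-treating or re-dosing a subject that had previously received treatment with EN3835". It does not restrict the earlier exposure to the parent study.

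Section 12.1.4 states: "If a subject received placebo in the double-blind study, she may be eligible for 2 treatment courses in the open-label study". It then classifies the second of these courses: "For the second treatment course, if the same quadrant is treated, subjects will be in the re-treatment arm", and "if a different quadrant is treated, subjects will be considered in the re-dosing arm".

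Section 17.2 classifies subjects, not courses, into one of four cohorts. Cohort 2 is "Re-treatment subjects - subjects who received EN3835 in study EN3835-201 and receive EN3835 in the current study in the same quadrant". Cohort 3 is "Re-dosing subjects - subjects who received EN3835 in study EN3835-201 and receive EN3835 in the current study in a quadrant different". Cohort 4 is "Initial treatment subjects - subjects who received placebo in study EN3835-201 and receive EN3835 in the current study". All efficacy and safety analyses are to be done within cohort.

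Section 17.5 has cellulite assessments evaluated separately by quadrant when an initial treatment subject has two quadrants treated. Section 17.6 summarizes AEs by treatment group without defining the term, and 17.6.4 counts a subject once per preferred term. Section 17.7 presents antibodies from Days 1, 71 and 360 "at each time point by region treated and overall".

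**The concern.** A former placebo subject on her second course is re-exposed to EN3835, and 12.1.4 says so. Under 17.2 she cannot enter cohort 2 or 3, because both require EN3835 in EN3835-201. Her second-course safety data are then counted as Initial treatment, together with first exposures.

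Two things are at stake. The AE rate in the Initial treatment cohort no longer describes a first course, and the re-exposure cohorts lose subjects who bear directly on the objective. Section 12.1.4.2 describes EN3835 as a foreign protein, so first and repeat exposure need to be told apart. Section 10.1 permits the second course from 28 days after the first ends, while 12.1.3 has former active subjects complete an observation visit first. Short-interval re-exposures may therefore sit mainly in the Initial treatment cohort.

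The objective also names immunogenicity, and 17.7 specifies no comparison of previously exposed with naive subjects.

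**Working it through.** No figure in the plan needs reproducing: the planned size of approximately 350 has no formula behind it, and this point does not depend on it. The check compares texts and then illustrates the size.

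**Classification of a former placebo subject**

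| Course in EN3835-202 | 12.1.4 | 17.2 |
|---|---|---|
| First | Treatment arm | Initial treatment |
| Second, same quadrant | Re-treatment arm | Initial treatment |
| Second, different quadrant | Re-dosing arm | Initial treatment |

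The last two rows conflict. The quadrant rule in 17.5 helps only for cellulite endpoints and only when the quadrants differ. It does not reach AEs, antibodies or a second course in the same quadrant. Because treatment group in 17.6 is undefined, it could mean the 17.2 cohorts or the 12.1.4 arms. Under the once-per-term count in 17.6.4, a second-course event can merge with a first-course event of the same term.

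**Antibodies.** The stated cuts are time point, region and overall. Days 1 and 71 are not labelled by course, so a two-course subject can have two Day 71 values with no rule for choosing between them. Footnote m to Table 3 omits the second-course Day 1 sample when Screening B or Day 1 of that course falls on Day 71 of the first. Section 10.1 gives such a Screening B as its example. A first-course Day 360 sample can also fall after a second course.

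**AE illustration.** Let p be the AE risk per course, equal and independent across courses, and u the share of treated former placebo subjects who take a second course. Neither is in the documents.

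Cohort rate = (1 − u)·p + u·[1 − (1 − p)²]

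- p = 0.10, u = 0.10: 0.9 × 0.10 + 0.1 × 0.19 = 0.109
- p = 0.10, u = 0.50: 0.5 × 0.10 + 0.5 × 0.19 = 0.145
- p = 0.20, u = 0.10: 0.9 × 0.20 + 0.1 × 0.36 = 0.216
- p = 0.20, u = 0.50: 0.5 × 0.20 + 0.5 × 0.36 = 0.28

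**Subjects affected.** EN3835-201 randomized 350 women 1:1 (section 8.3.1.4), so 350 / 2 = 175 were on each arm. This assumes all of them enroll.

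- Assume 60% to 100% of former placebo subjects are treated and 10% to 50% of those take a second course. Low: 175 × 0.6 × 0.1 = 10.5. High: 175 × 1.0 × 0.5 = 87.5.
- Assume 30% to 60% of former active subjects are re-exposed: 175 × 0.3 = 52.5 to 175 × 0.6 = 105 in cohorts 2 and 3.
- Share of all re-exposed subjects placed in Initial treatment: 10.5 / (10.5 + 105) = 9% to 87.5 / (87.5 + 52.5) = 62.5%.

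**The case against.** The strongest reply is that the plan does address re-exposure. Cohorts 2 and 3 consist entirely of re-exposed subjects, safety is analyzed within cohort, and the rationale in 8.6 frames re-exposure safety on women treated in EN3835-201. This stands. A reader might infer that the objective is not answered at all, and the documents do not support that: the safety half is answered for former active subjects.

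A reader might also infer that 17.7 necessarily pools naive and previously exposed subjects at Day 1. That does not follow either. The synopsis lists immunogenicity among the safety assessments, so the within-cohort rule could be read to cover it, with region as a cut inside each cohort. Against this, both the synopsis statistical methods and 17.7 treat immunogenicity under its own heading. The antibody summary by prior exposure is unspecified, not ruled out. Even on the favorable reading, cohort 4 would still mix first and second courses.

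The undefined treatment group in 17.6 likewise leaves room for AE tables by the 12.1.4 arms. That would contradict the cohort rule in 17.2, so a choice still has to be made.

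Finally, the protocol refers to a separate SAP for criteria for potentially clinically significant values (17.6.5 and 17.6.6). Its text is not among the documents available here, so whether it settles the grouping cannot be checked.

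**Conclusion.** The contradiction between 12.1.4 and 17.2 is certain on the text, and the same wording stands in Amendment 3. Followed as written, 17.2 counts former placebo subjects' second exposures as Initial treatment. The treatment group in 17.6 is tied to neither scheme, and 17.7 specifies no antibody summary by prior exposure or course. The re-exposure objective is incompletely answered; it is not unanswered.

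The size is illustrative only. With a 10% risk per course and 10% to 50% second-course uptake, the Initial treatment cohort shows about 10.9% to 14.5% instead of 10%. This assumes equal, independent risks and AE tables that follow the 17.2 cohorts. If risk differs on re-exposure, the distortion changes and the cohort table would not reveal it. The point merits correction because a stated rule misgroups data that bear on a stated objective.

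**What to change.** Use one course-level classification in 12.1.4, 17.2 and 17.6:

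- first EN3835 course;
- second course, same quadrant;
- second course, different quadrant;
- second courses also shown by whether the first was in EN3835-201 or EN3835-202.

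Define treatment group in 17.6 as these groups, and attribute each AE to the most recent course started.

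In 17.7, add percent positive and log titer by these groups at the pre-course sample and at Day 71 of each course, with change from the pre-course value. Where footnote m omits the second-course Day 1 sample, use the first-course Day 71 sample as the second-course baseline. Assign Day 360 samples to the most recent course received, so that samples taken after a second course are not reported as first-course results.

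The cost is wording and some extra programming, with no new visits or samples. A subject can appear in two course rows, which a table footnote should explain.
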